7.0 EXPLORATORY ENDPOINTS

The primary outcomes are wart-level endpoints that account for within-subject correlation. The exploratory endpoints are patient-level calculations of these endpoints, which lack sufficient statistical power for formal hypothesis tests.

7.1 Exploratory Efficacy Endpoint

7.1.1 Subject-level clearance of all warts at 30 days post last treatment

The number and percent of subjects with all warts “resolved” at 30 days post last treatment and the number of subjects with at least 1 wart “not resolved” at 30 days post last treatment will be calculated.

7.2 Exploratory Safety Endpoints

7.2.1 Subject-level wound healing adverse events at 30 days post last treatment

The number and percent of subjects with any wound healing event in any wart (composite of scabbing, swelling, crusting, blister, scar or ulcer) and no wound healing events in any wart at 30 days post last treatment will be calculated.

7.2.2 Subject-level skin change adverse events at 90 days post last treatment

The number and percent of subjects with any skin change event in any wart (scar, hypopigmentation or hyperpigmentation) and no skin change events in any wart at 90 days post last treatment will be calculated.

8.0 CLINICAL PHOTOGRAPHY

The Canfield Handheld 2D Imaging System and the Canon SL2 camera with ranging lights and MM Scale will be provided by the photography vendor, Canfield Scientific, Inc. (Parsippany, NJ) to document Investigator selected warts at enrollment, post treatment and at 7-days, 30-days, 60-days, and 90- days following the last CellFX treatment or Cryosurgical procedure. All consenting subjects’ study photographs will be captured using the equipment, supplies, and guidelines provided by Canfield to have consistent visual representation of the AD appearance during the study treatment. Images will be captured, viewed, and uploaded using Canfield Capture software which automatically checksums, encrypts, packages, and transfers the data to a secure, validated, and compliant web server hosted by Canfield. Detailed instructions for all aspects of the photography procedures will be supplied separately in the investigator user manual to be provided by Canfield.

9.0 INDEPENDENT PANEL REVIEW

To meet the requirements of the secondary endpoint, an Independent Panel will evaluate the treatment response from each study device. In order to enhance objectivity and reduce potential for bias, the Panel shall be independent of the Sponsor as well as the study sites/investigators.

The Panel is made up of three clinicians with pertinent expertise in dermatology who are not participants in the study and who do not have any other real or potential conflicts of interest. The Panel will be provided photographs of all treated warts at baseline and 30 days post last treatment and will be trained on specific criteria used to classify the response to treatment as noted in study **Section 6.1.2**.

An Independent Panel review will be conducted by Canfield Scientific based on prior standard methodology.

10.0 ADVERSE EVENTS

Pulse Biosciences will classify each reported Adverse Event according to ISO 14155:2011. All protocol specific AEs, whether device-related or not, will be recorded on the AE case report form and reported. Data to be collected will include the description of the AE, onset, and resolution dates (or whether the AE is ongoing), severity, management/treatment, outcome, and determination of the relationship to the device and/or procedure. All AEs related to a treated wart should be reported and classified by the blinded site Investigator and to be followed by the treating Investigator to determine the relationship of the AE to the device or the study procedure.

All AE information will be collected at each study visit from enrollment through 90 days following the last CellFX and Cryosurgical procedures. All AEs will be followed until the event has resolved (in the case of permanent impairment, the event will be followed until it stabilizes, and the overall clinical outcome has been ascertained).

When reporting AEs/SAEs, the Investigator should include the following information:

- Description of event
- Onset of event
- Duration of event
- Severity
- Relationship to device or procedure
- Action taken
- Subject outcome

Severity describes the intensity of an event and will be assessed as:

- **Mild:** The AE does not interfere in a significant manner with the subject's normal functioning level.
- **Moderate:** The AE produces some impairment of function but not hazardous to health.
- **Severe:** The AE produces significant impairment of function or incapacities and/or it is a hazard to the subject.

Relationship to device or procedure will be assessed as:

- **Unlikely:** There is no indication that the AE was caused by the investigational or standard of care device.
- **Possibly:** It cannot be excluded that the AE was caused by the investigational or standard of care device.
- **Likely:** A causal relationship between the investigational or standard of care device and the AE is at least a reasonable possibility; i.e. there is evidence or argument suggesting a causal relationship.

10.1 Adverse Event Definitions

10.1.1 Adverse Event (AE): (ISO 14155:2011 3.2)

Any untoward medical occurrence, unintended disease or injury, or untoward clinical signs (including abnormal laboratory findings) in subjects, users, or other persons, whether or not related to the investigational medical device.

NOTE 1: This definition includes events related to the investigational medical device or the comparator.

NOTE 2: This definition includes events related to the procedures involved.

***For the purposes of this protocol, only dermatologic AEs will be reported to the Sponsor.**

10.1.2 Adverse Device Effect (ADE): (*ISO 14155:2011 3.1*)

Adverse event related to the use of an investigational medical device

NOTE 1: This definition includes adverse events resulting from insufficient or inadequate instructions for use, deployment, implantation, installation, or operation, or any malfunction of the investigational medical device.

NOTE 2: This definition includes any event resulting from use error or from intentional misuse of the investigational medical device

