A total of 62 subjects and 267 study warts (195 treated and 62 sham controls) with an average of 4.1 warts per subject were enrolled and evaluated at 60-days post last treatment. Forty-two subjects were female (68%) and 20 were male (32%) with an average age of 47.3. Fitzpatrick skin types were distributed across Type I (5%), Type II (44%), Type III (32%) and Type IV (19%). More than 70% of all treated warts were located on the hands, knee, ankle, arm, leg, neck, and torso while the remaining 30% were plantar warts. Pre-treatment with intralesional injection of sodium bicarbonate buffered 1-2% lidocaine with 1:100,000 epinephrine was used to control pain (mean, 1.0ml). Subjects reported a median 4.0 at the time of treatment based on a 11-point visual pain scale, with 47.8% reporting a score of 0 or 1.

Overall efficacy at 60-days post-last treatment showing greater than 90% reduction in size was observed in 77.4% of common (72/93) and 43.8% of plantar warts (14/32). Single treatment efficacy at 60-days post-last treatment showed 81% (51/63) in patients with common warts and 31.6% (6/19) with plantar warts. Subject satisfaction at the end of study was reported in 73.7% (98/133) of subjects being satisfied with final results. As previously described in the wart feasibility study, there were 11 sham control warts (17.7%) showing 100% reduction in size. A total of 31 cases of transient hyperpigmentation (22.8%); 61% mild, 35% moderate, 3% mod/severe and 8 observations of hypopigmentation (5.9%) were observed at 60-days post-last treatment. No serious adverse events were reported however, 9 treatment-related adverse events (6 mild and 3 moderate severity) of transient pain, numbness, or infection were reported. These AEs occurred on the hands (n=5) or plantar area (n=4) and all were resolved with no associated sequela.⁸

This new wart comparison study under Protocol NP-WC-015 will evaluate safety and efficacy using the CellFX System with pre-defined treatment energy profiles for all primary and secondary treatments based on the tip size. The comparator group will be treated with cryosurgery with liquid nitrogen for the treatment of warts.

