10.1.3 Serious Adverse Event (SAE) (*ISO 14155:2011 3.37*)

Adverse event that

- a) led to death,
- b) led to serious deterioration in the health of the subject, that either resulted in
 - 1) a life-threatening illness or injury, or
 - 2) a permanent impairment of a body structure or a body function, or
 - 3) in-patient or prolonged hospitalization, or
 - 4) medical or surgical intervention to prevent life-threatening illness or injury or permanent impairment to a body structure or a body function,
- c) led to fetal distress, fetal death or a congenital abnormality or birth defect.

NOTE 1: Planned hospitalization for a pre-existing condition, or a procedure required by the CIP, without serious deterioration in health, is not considered a serious adverse event.

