10.1.4 Serious Adverse Device Effect (SADE): (*ISO 14155:2011 3.36*)

Adverse device effect that has resulted in any of the consequences characteristic of a Serious Adverse Event

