10.3.3 Investigator Responsibilities

The Investigator is responsible for reporting adverse events, including device malfunctions and device deficiencies as defined in the protocol. **Table 4** summarizes the time sensitive requirements for reporting adverse events and device deficiencies. The Sponsor is the contact person for these reporting requirements.

Table 4: Investigator Responsibilities for Submitting Adverse Events to the Sponsor

Type of Adverse Event	Reporting Timeframe
*Serious Adverse Device Effects (SADE), including Unanticipated Serious Adverse Device Effect (USADE) and dermatological events as described in section 9.3.2.1	As soon as possible, but in no case later than 3 calendar days after the clinical site first learns of the event or of new information in relation with an already reported event
**Serious Adverse Events (SAE)	As soon as possible, but in no case later than 3 calendar days after the clinical site first learns of the event or of new information in relation with an already reported event
Adverse Device Effects (ADE)	As soon as possible, but in no case later than 3 calendar days after the clinical site study team first learns of the event or of new information in relation with an already reported event
All other AEs	Submit in a timely manner after the clinical site first learns of the event

Type of Adverse Event	Reporting Timeframe
**Device Deficiency with SADE potential	As soon as possible, but in no case later than 3 calendar days after the clinical site study team first learns of the deficiency or of new information in relation with an already reported deficiency
All other Device Deficiencies	Submit in a timely manner after the clinical site first learns of the deficiency

*The Sponsor will report the results of an evaluation of an unanticipated serious or serious adverse device effect to the FDA and all reviewing IRBs and investigators within 10 working days after the Sponsor first received notice of the adverse effect per 21 CFR 812.150.

**It is the responsibility of the investigator to inform their IRB of serious adverse events and device deficiencies as required by their IRB guidelines.

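### The note in 10.1.1 limits reporting to the sponsor to dermatologic AEs, Table 4 does not, and nothing says which governs serious or device-related events outside the skin

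*Combined protocol and SAP*

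**What the plan says.** Section 10.1.1 defines an adverse event broadly, as "Any untoward medical occurrence, unintended disease or injury, or untoward clinical signs", whether or not the device is involved. A starred note at the end of that section, just before the 10.1.2 heading, then narrows what leaves the site: "For the purposes of this protocol, only dermatologic AEs will be reported to the Sponsor". The note has no exceptions.

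Table 4 in section 10.3.3 lists what the investigator submits to the sponsor, and when. For SADEs/USADEs and for SAEs the limit is "As soon as possible, but in no case later than 3 calendar days after the clinical site first learns of the event". The ADE row carries the same 3-calendar-day limit. A further row has all other AEs submitted promptly, with no fixed number of days. None of these rows is restricted to skin events.

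Section 10.0 sets the general scope: "All protocol specific AEs, whether device-related or not, will be recorded on the AE case report form and reported". It does not define which AEs are protocol specific. It adds that AEs related to a treated wart are to be reported and classified by the blinded site investigator, with no dermatologic qualifier.

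**The concern.** Two instructions to the same site staff, about the same recipient, give opposite answers for an event that is serious or device-related but not dermatologic. A site that follows the note keeps the event; a site that follows Table 4 sends it within 3 days.

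This matters because the protocol itself recognises hazards beyond the skin. It excludes subjects with implanted electronic devices and those allergic to lidocaine (4.2.2), and it gives local anesthetic with CellFX only (3.4, 4.5.3). Section 3.1 includes among the objectives the documentation of all safety issues that may count as adverse side effects or SAEs.

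Later steps also depend on the first report. Under the footnote to Table 4, the sponsor has 10 working days to report its evaluation of a serious or unanticipated device effect, counted from when it first received notice. An event that is not sent never starts that clock. The independent Safety Monitor in 10.3.2 oversees dermatological events, so that role is no backstop for other events.

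**Working it through.** No arithmetic applies, so the check sets the texts side by side.

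**1. Does the note reach serious and device-related events?** On a literal reading it does.
- An ADE is defined in 10.1.2 as "Adverse event related to the use of an investigational medical device".
- An SAE in 10.1.3 is an adverse event with certain outcomes. They include death, hospitalization and events that "led to fetal distress, fetal death or a congenital abnormality or birth defect", none of which is inherently dermatologic.
- A SADE in 10.1.4 is "Adverse device effect that has resulted in any of the consequences characteristic of a Serious Adverse Event".

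These three categories are built from the AE definition, so a limit placed on AEs carries over to them unless an exception is written. None is. The UADE definition in 10.1.5 is not limited to the skin either.

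**2. Could Table 4 be confined to skin events?** Its text does not support that. The first row names the dermatological stopping-rule events in addition to SADEs, which would be unnecessary if the whole table already concerned the skin. The SAE, ADE and all-other-AEs rows carry no qualifier.

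**3. Outcome under each text**

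| Event | 10.1.1 note, read literally | Table 4 |
|---|---|---|
| Dermatologic, any category | Sent | Sent; timing by category |
| Non-dermatologic SADE or USADE | Not sent | Within 3 calendar days |
| Non-dermatologic SAE, not device-related | Not sent | Within 3 calendar days |
| Non-dermatologic ADE, not serious | Not sent | Within 3 calendar days |
| Other non-dermatologic AE | Not sent | Sent; no fixed limit |

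The texts differ in all four non-dermatologic rows, including the last.

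**4. Is there a rule of precedence?** None appears in sections 10.0 to 10.3.3, nor in 12.2, which only points back to the safety reporting section.

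**5. What does section 10.0 rescue?** AEs related to a treated wart are to be reported whatever their nature. The same section says the sponsor classifies each reported AE, so reporting there is naturally read as reaching the sponsor. The exposed set is therefore non-dermatologic events not tied to a treated wart: serious, systemic or anesthetic-related events, and routine unrelated ones.

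**6. Does the exposure differ by arm?** For anesthetic-related events it does. Section 4.5.3 restricts anesthesia to CellFX-treated warts, so such events can arise only in that arm.

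**7. Are the trial's formal endpoints touched?** No. The co-primary endpoints (6.1) are wart-level findings by the blinded site investigator and do not depend on what the AE form sends to the sponsor. The same holds for the lesion observations (6.2) and the subject-level safety summaries (7.2).

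**The case against.** The best defence is that the note sits under the general AE definition, while SAE, ADE, SADE and UADE have their own headings without it. On that view Table 4 is the operative instruction for those categories and the note limits only routine AEs. A dermatologic focus for routine events would also fit the Safety Monitor's remit. This is a natural reading, and it is why the point is that a site could withhold such events, not that it would. It does not settle the matter, because no sentence states that precedence and the all-other-AEs row conflicts with the note even for routine events.

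The opposite defence is that Table 4 sets timing only for events already reportable, since 10.0 speaks of protocol-specific AEs and 10.3.3 refers to definitions in the protocol. The first term is never defined. If this reading were right, non-dermatologic serious events would indeed go unreported.

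There are partial backstops. Monitors review events meeting SAE reporting criteria (11.5.2), although that rests on the disputed rule. Morbidity and mortality are reviewed with investigators (12.2). The sponsor commits to ISO 14155 and Part 812 (11.1), and investigators inform their IRBs of SAEs (Table 4 footnote). These lower the risk without removing the conflict.

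A reader might go further and infer from the prior study, where "9 treatment-related adverse events (6 mild and 3 moderate severity) of transient pain, numbness, or infection were reported", that most such events would now be lost. The documents do not support this. Those nine events were on the hands (5) or plantar area (4), both wart sites in that study. If they arose at treated warts, the wart-related sentence in 10.0 would cover their like here. The split between pain, numbness and infection is not given. Nothing indicates that sites would regard wart-site pain or numbness as non-dermatologic. Pain, numbness and muscle twitching are also collected on schedule (3.2, 3.4, 4.4, 4.5.3 and the retreatment visits). Those checks occur at fixed times and do not replace AE reports, but the symptoms would not disappear from the data.

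**Conclusion.** The inconsistency is real and lies in the wording. The 10.1.1 note and Table 4 give incompatible instructions for non-dermatologic events, and no text ranks them. The consequence that can be supported is limited: a site could treat the note as permission not to send serious, systemic or anesthetic-related events unconnected with a treated wart. For anesthetic-related events, any omission would fall on the CellFX arm.

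The number of events at risk cannot be estimated from the documents. The conclusion rests on reading the note literally and on the wart-related sentence in 10.0 operating as written.

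A reader might also infer that the trial's between-arm safety comparison is compromised. That does not follow: the co-primary safety endpoints are blinded skin assessments that do not depend on the note, and no formal between-arm comparison of non-dermatologic AEs is planned. What is exposed is general safety reporting, including the start of the sponsor's 10-working-day clock. That warrants correction.

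**What to change.** Add a sentence to the 10.1.1 note saying that the dermatologic-only limit does not apply to SAEs, ADEs, SADEs, UADEs, procedure-related events or device deficiencies, all of which go to the sponsor regardless of body system. Then bring the other two places into line: define in 10.0 what counts as a protocol-specific AE, and word the all-other-AEs row of Table 4 to match whatever limit is kept for routine AEs that are neither serious nor related.

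In the same edit, correct the cross-references. Table 4 points to section 9.3.2.1 and section 12.2 to section 9.3, whereas the stopping rules and safety reporting are in 10.3.2.1 and 10.3.

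The cost is a short text change and a small amount of additional AE reporting by sites. The endpoints, sample size and visit schedule do not change.

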10.1.3 Serious Adverse Event (SAE) (*ISO 14155:2011 3.37*)

Adverse event that

- a) led to death,
- b) led to serious deterioration in the health of the subject, that either resulted in
 - 1) a life-threatening illness or injury, or
 - 2) a permanent impairment of a body structure or a body function, or
 - 3) in-patient or prolonged hospitalization, or
 - 4) medical or surgical intervention to prevent life-threatening illness or injury or permanent impairment to a body structure or a body function,
- c) led to fetal distress, fetal death or a congenital abnormality or birth defect.

NOTE 1: Planned hospitalization for a pre-existing condition, or a procedure required by the CIP, without serious deterioration in health, is not considered a serious adverse event.

10.1.4 Serious Adverse Device Effect (SADE): (*ISO 14155:2011 3.36*)

Adverse device effect that has resulted in any of the consequences characteristic of a Serious Adverse Event

10.1.5 Unanticipated Adverse Device Effect (UADE): (*21CFR812.3*)

Any serious adverse effect on health or safety or any life-threatening problem or death caused by, or associated with, a device, if that effect, problem, or death was not previously identified in nature, severity, or degree of incidence in the investigational plan or application, or any other unanticipated serious problem associated with a device that relates to the rights, safety, or welfare of subjects.

10.2 Device Deficiencies (*ISO 14155:2011 3.15*)

10.2.1 Definitions

Device Deficiency is an Inadequacy of a medical device with respect to its identity, quality, durability, reliability, safety, or performance.

NOTE: Device deficiencies include malfunctions, use errors, and inadequate labelling.

Device Malfunction is a failure of the study device to perform in accordance with its intended purpose when used in accordance with the instructions for use or study protocol.

10.3 Safety Reporting Requirements

The following sections will summarize the safety reporting requirements for the Sponsor and site Investigators. The NP-WC-015 IDE study will also include an early safety assessment on the first 20 subjects treated with CellFX.

10.3.1 Blinded Live Assessment of Adverse Events

The Blinded Investigator from each of the clinical research sites will conduct a live safety assessment on all enrolled subjects at each study visit. The blinded investigator will ensure that all adverse events that are related to the stopping rules in **Section 10.3.2.1** are reported to the Sponsor within three calendar days.

10.3.2 Safety Monitor

The Sponsor will select an independent Safety Monitor to oversee dermatological adverse events. The First 20 subjects who are treated with CellFX will have their data analyzed when they complete the 30 day follow up visit or 30 days post initial treatment. A table describing the 30 days status of the subjects will be prepared. Adverse events will be presented as the percentage of subjects who experience an event, the number of events and the event rate per 30 days. The photographic images of the dermatological adverse events will also be presented to the Safety Monitor.

